## 2. LIST OF ABBREVIATIONS

AUC	Area Under the Curve
sVCAM-1	Soluble Vascular Cell Adhesion Molecule-1
vWF	von Willebrand Factor
sICAM-1	Soluble Intercellular Adhesion Molecule-1
FMD	Flow Mediated Dilation
GABR	Global Arginine Bioavailability Ratio
AOR	Arginine to Ornithine Ratio
T2DM	Diabetes Mellitus Type 2
DPP4	Dipeptidylpeptidase IV
OD	Once daily
MTT	Meal Tolerance Test
CAD	Coronary Artery Disease
UKPDS	United Kingdom Prospective Diabetes Study
GLP-1	Glucagon like-peptide-1
HbA1c	Glycated haemoglobin
AST	Aspartate-Aminotransferase
ALT	Alanine-Aminotransferase
oGTT	Oral glucose tolerance test
GTN	Glyceroltrinitrate

### 3. AMENDMENT HISTORY

Amendment No.	Protocol Version No.	Date issued	Author(s) of changes	Details of Changes made
1	2.1	05.Aug.2013	[name], [name]	1)MTT (Fortimel compact instead of Fortisip liquid) 2)Combination of Screening and Baseline visits 3) Blood storage
2	2.2	22.Oct.2013	[name], [name]	1)Blood sampling 2)Inclusion criteria: (Age 40 to 80 years)
3	2.3	30.April 2014	[name], [name]	1)Exclusion criteria: HbA1c <6.0% (42mmol/mol) instead of HbA1c <6.5 (48mmol/mol)
4	2.4	24.October 2014	[name], [name]	1)Storage of blood samples in the Biobank

### 4. SYNOPSIS

Study Title	Effects of linagliptin on endothelial function and global arginine bioavailability ratio in coronary artery disease patients with early diabetes
Study Design	Randomised, double-blind, placebo-controlled, parallel group trial
Study Participants	Subjects at early stages of type 2 diabetes
Number of Participants	50
Follow-up duration	3 months
Planned Duration	16 months

Primary Objective	The primary objective is to investigate the impact of a 12 week linagliptin treatment on endothelial function in patients with early T2DM.
Secondary Objectives	The secondary objective is to investigate the effect of a 12 week linagliptin treatment on 

- arginine bioavailability ratios (global arginine bioavailability ratio and arginine to ornithine ratio)

- biochemical markers of endothelial function (sVCAM-1, sICAM-1, vWF)

- the AUC of glucose, insulin and free fatty acids during the meal tolerance test

## 5. BACKGROUND AND RATIONALE

Patients with type 2 diabetes (T2DM) are at increased risk of macrovascular events as well as microvascular complications (1). It is well known, that the pathophysiologic process of type 2 diabetes starts many years before the diagnosis can be made on the basis of elevated fasting blood glucose.(2) In particular the data of the UKPDS study and the UKPDS post trial monitoring highlighted the importance of an early glucose lowering intervention in patients with T2DM with respect to micro- and macrovascular complications. (3, 4)

We (5,6) and in particular the Euro Heart survey on Diabetes and the Heart (7) demonstrated, that in a cardiovascular high risk population, namely patients with coronary artery disease (CAD), about 35% suffer from manifest type 2 diabetes. In addition, another 9 to 15% of CAD patients have postchallenge diabetes, diagnosed on the basis of an oral glucose tolerance test, which means that approximately a half of all patients with CAD have diabetes.

Recently we could demonstrate that not only established type 2 diabetes diagnosed on the basis of fasting hyperglycaemia is associated with an increased cardiovascular risk, but also postchallenge hyperglycemia (i.e. impaired glucose tolerance or postchallenge diabetes).

Dipeptidylpeptidase-4 (DPP-4) inhibitors increase endogenous glucagon like-peptide-1 (GLP-1) levels and GLP-1 in turn increases the insulin release from pancreatic beta-cells in a glucose dependent manner as well as suppresses glucagon secretion from pancreatic alpha cells. Investigations in type 2 diabetic patients showed that this drug class lowers both, fasting and postchallenge or postmeal glucose levels and hence, HbA1c and is well tolerated.

However, the lowering of the surrogate measurement HbA1c has not necessarily turned out to translate into a reduced number of cardiovascular events in patients with T2DM. In contrary in particular for the thiazolidinedione Rosiglitazone concerns about an increased risk of cardiovascular events have been raised despite a robust HbA1c lowering effect. (8) Therefore the FDA (9) and the EMA (10) issued in 2008 and 2010, respectively, guidance for new glucose lowering drugs, requiring proof of at least cardiovascular safety. Cardiovascular outcome trials with Linagliptin are currently being performed (CAROLINA, CARMELINA), however, it will take a couple of years until the results are available.

A well known and validated cardiovascular surrogate parameter is endothelial dysfunction. We and others have shown previously, that endothelial dysfunction is present in patients with coronary artery disease and early diabetes and can be improved by pharmacological intervention. (11, 12) This surrogate measurement could be helpful in better understanding the cardiovascular effects of Linagliptin while awaiting the results of the definitive outcome trials.

The aim of our current study is to investigate the effects of Linagliptin in coronary patients with early T2DM on various cardiovascular surrogate measurements including mechanical and biochemical endothelial function assessments.

## **6. AIMS OF THE STUDY**

The overarching aim of our study is to investigate the effects of Linagliptin on endothelial function, arginine bioavailability ratios and postchallenge glycaemic control in patients with early diabetes and coronary atherosclerosis.

## **7. OBJECTIVES**

### **7.1 Primary objective**

The primary objective is to determine whether a 12 week Linagliptin treatment is associated with an improvement in endothelial function in patients with early diabetes.

### **7.2 Secondary objective**

The secondary objective is to investigate the effect of a 12 week Linagliptin treatment on

- arginine bioavailability ratios (global arginine bioavailability ratio and arginine to ornithine ratio)
- biochemical markers of endothelial function (sVCAM-1, sICAM-1, vWF)
- the AUC of glucose, insulin and free fatty acids during the meal tolerance test

## **8. OUTCOMES**

### **8.1 Primary outcome**

*Changes in endothelial function (assessed by flow mediated dilatation – FMD) by a 12 week*

*Linagliptin treatment in patients with early T2DM.*

### **8.2 Secondary outcome parameters**

[figure not shown]
- Changes in arginine bioavailability ratios (global arginine bioavailability ratio and arginine to ornithine ratio)
- Changes in biochemical markers of endothelial function (sVCAM-1, sICAM-1, vWF)
- Changes in the AUC of glucose, insulin and free fatty acids during the meal tolerance test

## **9. STUDY DESIGN**

This is a single-centre, prospective, randomized, double-blind, placebo-controlled, parallel group 12 week clinical trial evaluating the effect of Linagliptin 5mg OD orally on cardiovascular surrogate measures in patients with early diabetes. 50 subjects will be randomised to receive either Linagliptin or placebo for 12 weeks. At baseline all subjects will undergo endothelial function assessment (FMD), blood sampling as well as a meal tolerance test. At the end of the 12-week treatment period all subjects will undergo a repeat FMD, blood sampling as well as a meal tolerance test.

### 9.1 Schematic overview on study design

### 9.2 Duration of Study

It is anticipated that the study will run for 16 months (from first patient first visit until last patient last visit).

### 9.3 Source Data

Source documents comprise the CRF and hospital records, laboratory records and correspondence.

All documents will be stored safely in a confidential manner. The subject will be referred to by a unique study subject number/code, their initials and date of birth on all study-specific documentations. The only exceptions will be the signed Consent Forms, Subject Identification log and subject clinical file, all of which will be stored securely by the clinical site.

Source data will be made available for internal and external audits or inspections by regulatory authorities to authorised personnel only.

#### **9.4 Randomisation and Blinding**

The randomisation plan will be designed by the Institute of Medical Informatics, Statistics and Documentation, Medical University Graz, Austria, which will pass the randomisation list to the Pharmacy of the University Hospital Graz for adequate labelling and blinding of the medication. The labels of the study medication will display the name of the trial, the name of the investigational medicinal product and contact details of the principal investigator.

Subject numbers will be assigned sequentially as each subject enters the study.

#### **9.5 Unblinding**

In the rare case of a requirement to unblind study medication, the Principal investigator will need give permission for unblinding. The unblinding list will be held by the Institute of Medical Informatics, Statistics and Documentation, Medical University of Graz, who is not involved in study investigations.

### **10. SELECTION AND WITHDRAWAL OF STUDY SUBJECTS**

#### **10.1 Subject Selection**

The study population will consist of

- 50 subjects with early diabetes (i.e. postchallenge diabetes (2h glucose >200 mg/dl or type 2 diabetes treated with diet only or on a stable dose of metformin monotherapy)

## 10.2 Subject Recruitment

Patients will be identified from the outpatient clinic at the Department of Endocrinology and Metabolism, the Division of Cardiology, via Primary Care and adverts.

## 10.3 Inclusion Criteria

- Age 40-80
- Early diabetes (postchallenge diabetes (2h glucose >200 mg/dl or type 2 diabetes treated with diet only or on a stable dose of metformin monotherapy)
- Coronary atherosclerosis (diagnosed via coronary angiography or coronary computer tomography)

## 10.4 Exclusion Criteria

- Acute coronary syndrome or cerebrovascular event within the previous 4 weeks
- BMI > 35 kg/m^2
- HbA1c <6.0% (42 mmol/mol)
- Serum creatinine > 2.5 mg/dl
- AST/ALT > 3x upper limit of normal
- HbA1c >9.0% (>75 mmol/mol)
- Heart failure > NYHA class II
- Uncontrolled hypertension (blood pressure > 165 / 100 mmHg)
- Treatment with orally administered steroids
- New onset statin or ACE-inhibitor within the previous 6 weeks
- Known Malignancy
- Pregnancy or breast feeding women.

### **10.5 Withdrawal / Drop out of subjects**

Each subject has the right to withdraw from the study at any time without prejudice or compromise to future care.

The investigator may discontinue or withdraw the subjects under the following circumstances:

- Significant protocol deviation
- Significant non-compliance with treatment regime or study procedures
- An adverse event that requires discontinuation of the study medication or results in inability to continue to comply with study procedures. If a subject is withdrawn due to an adverse event, the investigator will arrange for follow-up visits or telephone calls until the adverse event has resolved or stabilised.
- Consent withdrawn
- Lost to follow up
- The study will be stopped prematurely if any information relating to the IMP or any other aspect of the study arises that may cause harm to the participant.
- Any other situation that may, in the opinion of the investigator, make it unsafe or inappropriate for the subject to continue in the trial

A drop-out rate of 10% was considered in the sample size estimate. In case of further drop-outs additional recruitment has to take place to avoid loss of statistical power.

### **10.6 Payment to subjects**

Reimbursement of reasonable travel expenses will be considered.

### **10.7 End of study**

*The study end is defined as the last visit of the last patient. In the case of new data suggesting a significant safety concern of the study drug, the trial will be prematurely stopped.*

## 11 STUDY PROCEDURES

### 11.1 Schedule of study procedures

	Screening (V1)* (up to 1 month prior to baseline)	Baseline (V2) (week 0)	Follow-up (V3) (Week 12 ± 1)
Informed Consent	X		
Inclusion/exclusion criteria	X	X	
Randomisation		X	
Demography, medical history	X		
Concomitant medication	X	X	X
Vital signs	X	X	X
Physical examination		X	
Flow Mediated Dilatation (FMD)		X	X
GABR, biochemical markers of endothelial function (sVCAM-1, sICAM-1, vWF)		X	X
Blood sampling	X	X	X
Meal tolerance test (MTT)		X	X
Adverse Events			X
Dispense medication		X	
Drug accountability			X
Pregnancy test (females with childbearing potential)	X		X

**\*if blood samples to check inclusion/exclusion criteria are available within 4 weeks prior to randomisation, the screening visit and baseline visit can be performed on the same day**

## 11.2 Visit Schedule

### **Screening contact – Visit 1 (up to 1 month prior to potential randomisation)**

- Sufficient time will be provided and subjects will be encouraged to discuss all queries with the research team
- Informed consent will be obtained by an investigator
- Check inclusion and exclusion criteria
- Demographics will be obtained: date of birth, gender, race, smoking status, alcohol consumption
- Weight
- Height
- Medical history
- Concomitant medication
- Vital signs: resting pulse and blood pressure
- Blood sample for HbA1c
- Baseline safety blood tests (fasting): Full blood cell count, renal function tests, liver function tests
- Pregnancy test in female woman of childbearing age.

### **Baseline (week 0)**

- Review inclusion and exclusion criteria
- Vital signs
- Weight
- Physical examination
- Concomitant medication review
- FMD measurement
- Blood sampling for cardiovascular surrogate measurements
- Meal tolerance test
- Randomisation: patients will be randomised to either Linagliptin 5 mg or placebo for the next 12 weeks
- Dispense study medication.

### **Week 12 visit**

- Weight
- Vital signs
- Concomitant medication review
- Adverse events assessment
- FMD measurement
- Blood sampling for cardiovascular surrogate measurements
- Meal tolerance test
- Drug accountability.

### **Phone call 28 days after week 12 visit**

- Assessment of adverse events

### **11.3 Laboratory results**

All laboratory results will be reviewed and the reports signed by the study physician who will record whether it is normal, abnormal but not clinically significant, or abnormal and clinically significant. In the latter case, the eligibility of the subject will be reviewed.

## **12 METHODS**

### **12.1 Meal Tolerance Test (MTT)**

The MTT will be performed after an overnight fast (apart from water). A standard gauge cannula will be placed into a subcutaneous vein for blood sampling. In order to prevent blood clotting in the cannula and to keep the cannula working it will be occasionally flushed with sterile normal saline. Study medication will be given (time -15 mins) before the meal. A pre-meal blood sample will be taken (- 5mins) and then all subjects will be asked to drink Fortimel compact (10 kcal/kg) over a period of 2-4 mins (time 0 mins). During the meal test further blood samples will be taken at 15, 30, 60, and 120 minutes. All samples will be used for determination of glucose, insulin and free fatty acids. The blood at each time point will be placed into a fluoride oxalate tube (1ml) for plasma glucose and into a serum tube for insulin and free fatty acids.

### **12.2 Flow mediated dilation**

Endothelial dysfunction: Endothelium-dependent FMD following reactive hyperaemia and endothelium-independent NMD following administration of GTN are examined in the brachial artery according to the guidelines described by Coretti et al (13).

Using high resolution ultrasound measurements of the right brachial artery are taken after resting, after cuff deflation (250 mmHg for 5 minutes) of the forearm and after sublingual administration of 0.4 mg glyceroltrinitrate (GTN). Scans of the brachial artery are taken proximal to the antecubital fossa with simultaneous ECG recording. Diameter measurements are taken from one media-adventitia interface to the other for three to four times at baseline (the average is taken for calculating the baseline diameter), three times after 45 to 60 seconds after cuff deflation following reactive hyperaemia and four minutes after administration of GTN. GTN is applied 15 minutes after cuff deflation to allow arterial diameter to return to baseline, which will be controlled by measuring another baseline diameter.

FMD-diameter is calculated as the average of the three diameter measurements following reactive hyperaemia. FMD and NMD are calculated as the percent change in diameter compared to baseline.

### 12.3 Blood sampling

Over the 3 study visits in total approximately 51 ml of blood will be taken to determine the parameters outlined below. A potential remainder of serum and plasma will be stored anonymised (patient number and visit number only) at -80°C in the Biobank of the Medical University of Graz for potential future analyses.

Twice, at baseline and after 3 months, blood (8ml LiHep) will be taken to analyse the impact of linagliptin on the number and function of endothelial progenitor cells.

#### Laboratory measurements

Insulin and c-peptide will be measured by chemiluminescence on an ADVIA Centaur system (Siemens Healthcare Diagnostics, Eschborn, Germany). FFA will be measured enzymatically (Wako Chemical, Neuss, Germany) on an Olympus AU640 (Olympus Diagnostica, Hamburg, Germany). Routine parameters will be determined using a cobas® analyzer (Roche Diagnostics, Mannheim, Germany).

#### GABR

Arginine, ornithine and citrulline will be measured in serum samples with a conventional usual amino acid analysis technique, involving separation of amino acids by ion exchange chromatography followed by postcolumn continuous reaction with ninhydrin. Global arginine bioavailability ratio will be calculated by L-arginine divided by the sum of (L-ornithine plus L-citrulline). The arginine to ornithine ratio will be calculated by dividing L-arginine by L-ornithine levels.

### **12.4 Data analysis and sample size estimation**

#### Data analysis

Continuous variables will be presented as means, standard deviation, median, minimum and maximum, for categorical data frequencies and relative frequencies are used. To examine differences between groups at baseline, t-tests or Mann-Whitney U tests and chi-square tests will be used as appropriate. The primary outcome, FMD after 12 weeks, will be analysed using ANCOVA. Comparisons within groups will be performed using paired t-test or Wilcoxon rank-sum test. A p-value of <0.05 is considered to indicate

statistical significance. A statistical analysis plan will be prepared and finalized before database lock.

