#### Sample size

Sample size was estimated using free available calculator <http://www.quantitativeskills.com/sisa/calculations/samsize.htm>. Assuming an improvement of endothelial dysfunction of 30% (relative) and a SD of 3% (% FMD) a total of 42 subjects will be needed to detect this difference with an alpha of 0.05 and a power of 0.90. To account for a dropout rate of about 20% each group will consist of 25 patients.

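### The within-group non-parametric test is named as the Wilcoxon rank-sum test, which is for independent samples, although the data are paired

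*Protocol*

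**What the plan says.** Section 12.4 of the protocol (Data analysis) names tests for three purposes.

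- Baseline differences between the two arms: "To examine differences between groups at baseline, t-tests or Mann-Whitney U tests and chi-square tests will be used as appropriate".
- Primary outcome: "The primary outcome, FMD after 12 weeks, will be analysed using ANCOVA".
- Change within an arm: "Comparisons within groups will be performed using paired t-test or Wilcoxon rank-sum test".

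The threshold for significance is 0.05. Section 9 (Study design) fixes the data structure. For the first visit it says "At baseline all subjects will undergo endothelial function assessment (FMD), blood sampling as well as a meal tolerance test", and for the second "At the end of the 12-week treatment period all subjects will undergo a repeat FMD, blood sampling as well as a meal tolerance test". The schedule in section 11.1 shows the same two measurement times, V2 and V3.

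**The concern.** The within-group sentence offers a parametric and a non-parametric option for the same comparison. The parametric option, the paired t-test, uses the pairing. The non-parametric option does not: the rank-sum test compares two independent samples and is equivalent to the Mann-Whitney U test that the same paragraph assigns to the comparison of the two arms at baseline. One paragraph therefore gives the same test, under two names, to independent and to paired data.

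The sentence is not limited to FMD. It can apply to every outcome that section 8.2 defines as a change: the arginine ratios, sVCAM-1, sICAM-1, vWF, and the AUCs of glucose, insulin and free fatty acids. Ratios, biomarkers and AUCs may well be skewed, so the non-parametric option could be used. Software will run a rank-sum test on the two visit columns without complaint, so the error would not show itself. What is at stake is the validity of those p-values and the power to see a change within an arm.

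**Working it through.** The protocol gives no figure to reproduce on this point. The check is of the test named against the data structure, followed by a calculation of the consequence.

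**Inputs from the protocol**
- Paired data: the same subjects at baseline and week 12 (section 9).
- Significance level 0.05 (section 12.4); taken as two-sided, since the sidedness is not stated.
- Pairs per arm: 42/2 = 21, from "a total of 42 subjects will be needed to detect this difference with an alpha of 0.05 and a power of 0.90" (Sample size), or 25 if nobody drops out.
- SD of FMD: 3 percentage points (Sample size).

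**Assumptions, because the protocol gives no figure**
- Correlation ρ between the two visits: 0 to 0.7.
- True change within an arm: two-thirds of an SD (2 FMD points at SD 3), with half an SD (1.5 points) as a second case.

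**Why ignoring the pairing matters.** The argument is simplest for means. With n pairs and standard deviation σ at each visit:

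- variance of the mean change = 2σ²(1 − ρ)/n
- variance assumed when the visits are treated as independent = 2σ²/n

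The standard error used is too large by the factor 1/√(1 − ρ), so the real two-sided type I error is about 2Φ(−1.96/√(1 − ρ)):

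- ρ = 0.3: 1.96/0.837 = 2.34, giving 1.9%
- ρ = 0.5: 1.96/0.707 = 2.77, giving 0.6%
- ρ = 0.7: 1.96/0.548 = 3.58, giving 0.03%

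**Simulation of the rank tests themselves.** 20,000 data sets per cell, two-sided 0.05; rank-sum on the two visit columns, exact signed-rank on the differences. With 21 pairs, normal data and a change of two-thirds of an SD for power:

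| ρ | Type I, rank-sum | Type I, signed-rank | Power, rank-sum | Power, signed-rank |
|---|---|---|---|---|
| 0 | 5.0% | 4.6–4.9% | 54% | 51% |
| 0.3 | 2.1% | 4.6–4.9% | 54% | 66% |
| 0.5 | 0.8% | 4.6–4.9% | 55% | 80% |
| 0.7 | 0.1% | 4.6–4.9% | 57% | 95% |

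The range for signed-rank type I error covers all four correlations. The rank-sum column follows the approximation above.

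**Sensitivity**
- *Skewed data* (log-normal, exp(0.6z), shift on the z scale, 21 pairs): rank-sum type I error 5.1%, 2.1%, 0.9% and 0.1%; power 54–57% for rank-sum against 49%, 62%, 77% and 93% for signed-rank. The rank-sum results barely move because ranks do not change when both columns are exponentiated.
- *25 pairs*, normal data, two-thirds of an SD, ρ from 0.3 to 0.7: power 63–68% against 75–98%.
- *25 pairs, smaller change* of 1.5 points (half an SD; 10,000 data sets per cell), ρ = 0, 0.3, 0.5, 0.7: power 39%, 36%, 35% and 31% for rank-sum against 38%, 50%, 65% and 85% for signed-rank.

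**The case against.** The strongest reply is that this is a slip of the pen. The term stands beside the paired t-test in a sentence about within-group comparisons, and the authors call the independent-samples test Mann-Whitney U elsewhere in the paragraph. The different name suggests that they had a different, paired test in mind. Section 12.4 also promises a SAP before database lock. That SAP is not at hand and may already name the right test.

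The consequence is also narrow. The error makes the test conservative, so it creates no false positives over the correlations considered. In a randomised placebo-controlled trial, a change within one arm cannot by itself show a drug effect. The exact percentages depend on an assumed correlation and an assumed change: with a change of half an SD, rank-sum power falls as the correlation rises, whereas with two-thirds of an SD it rises slightly.

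Most of this stands as a limit on weight. The slip is likely, the percentages are illustrative, and only the direction is robust. None of it makes the sentence correct. The protocol does not leave the choice open: it names a real and different test, and no other section corrects it. A SAP that copied the name would carry the error forward, and one that used signed-rank would depart from the protocol. Section 12.4 also does not label the within-group tests as supportive, and it names no between-group test for the secondary outcomes at follow-up.

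**Conclusion.** The point holds: the test is wrong as written. For positively correlated visits the rank-sum option gives p-values that are too large on average. At an assumed correlation of 0.3 to 0.7 with 21 pairs and normal data, the real type I error is 2.1% down to 0.1% at a nominal 5%. The loss of power is 12 to 38 percentage points for a change of two-thirds of an SD (66 − 54 and 95 − 57). If the visits were uncorrelated there would be no material harm.

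The primary ANCOVA of FMD, the baseline comparisons between arms and the sample size do not depend on this sentence. It is a small correction, and it should be made because the text is definitely wrong and the change costs almost nothing.

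**What to change.** In section 12.4, Data analysis, replace the Wilcoxon rank-sum test by the Wilcoxon signed-rank test for within-group comparisons, and use the same name in the SAP. Leave the Mann-Whitney U test in place for the baseline comparison of the two arms.

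The cost is one word in the protocol and a check that the SAP agrees. No patients, visits, samples or other analyses are affected.
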